9.	PATIENT AND PUBLIC INVOLVEMENT (PPI).....	28
10.	DISSEMINATION AND PUBLICATION	29
11.	REFERENCES	30

LIST OF TABLES

PAGE

Table 1:	Criteria for progression from pilot study to main trial	133
Table 2	Trial assessments	200
Table 3	Pre-Specified Complications List (safety outcomes)	211

LIST OF FIGURES

PAGE

Figure 1	Trial flow diagram	122
Figure 2	Venner PneuX™ device - an advance airways protection system	188
Figure 3	PROTECT Airways Site and Recruitment Projection Chart	244

TRIAL SUMMARY

Master Protocol Title	CoReCCT - Confederation of Respiratory Critical Care Trials	
Trial Title	The clinical and cost effectiveness of advanced airways protection device versus conventional endotracheal tubes in intensive care unit patients requiring mechanical ventilation: a multi-centre, pragmatic, randomised clinical trial	
Internal ref. number (or short title)	PROTECT Airways	
Clinical Phase	Phase IV	
Trial Design	A multi-centre, pragmatic, individually randomised, open-label, parallel group trial, and economic evaluation, to determine the clinical and cost effectiveness of an advanced airways protection device, compared with conventional endotracheal tube (with or without basic subglottic suction and standard cuff) in hospitalised patients requiring mechanical ventilation.	
Trial Participants	Adult (age≥18), hospitalised needing mechanical ventilation, likely to remain ventilated for at least 24 hours following randomisation	
Planned sample size	2194 patients	
Planned Trial Period	Planned Start date 1st May 2024 63 months: 6-months set-up; 9-months internal pilot; 39-months recruitment; 6-months follow-up; 3-months data analysis, reporting and dissemination.	
	Objectives	Outcome Measures
Primary	To determine the clinical and cost effectiveness of an advanced airways protection device	Duration of mechanical ventilation as measured from time from randomisation to first successful unassisted breathing, measured in days (full definition in section 2.3)
Secondary	To determine the clinical and cost effectiveness of an advanced airways protection device	
 • Core clinical outcome set as per CoReCCT master protocol In addition to: 
 • Endotracheal intubation duration in hours • Ventilator Associated Pneumonia (VAP) • Hospital Acquired Pneumonia (HAP)

LIST OF ABBREVIATIONS/GLOSSARY

Abbreviation	Explanation
AE	Adverse Event
APACHE II	Acute Physiology And Chronic Health Evaluation II
CI	Chief Investigator
CACE	Compliers Average Causal Effect
CEACs	Cost Effectiveness Acceptability Curves
CONSORT	Consolidated Standards of Reporting Trials
CoReCCT	Confederation of Respiratory Critical Care Trials
COVenT	Core Outcomes in Ventilation Trials
CRF	Case Report Form
CTU	Clinical Trials Unit
DMC	Data Monitoring Committee
ETT	Endo Tracheal Tube
GCP	Good Clinical Practice
HAI	Hospital Acquired Infection
HES	Hospital Episode Statistics
HRQoL	Health Related Quality of Life
HTA	Health Technology Assessment
ICF	Informed Consent Form
ICNARC	Intensive Care National Audit & Research Centre
ICU	Intensive Care Unit
ICEs	Inter Current Events
ICER	Incremental Cost Effectiveness Ratio
IRAS	Integrated Research Application System
ISRCTN	International Standard Randomised Controlled Trial Number
ITT	Intention To Treat
MRC	Medical Research Council
NHS	National Health Service
NICE	National Institute of Health and Care Excellence
NIHR HTA	National Institute of Health and Care Research Health Technology Assessment
PI	Principal Investigator
PPI	Patient & Public Involvement
PSS	Personal Social Services
PVC	Poly Vinyl Chloride
QoL	Quality of Life
QALY	Quality Adjusted Life Years
RCT	Randomised Controlled Trial
REC	Research Ethics Committee
RUQ	Resource Use Questionnaires
R&D	Research and Development

SAE	Serious Adverse Event
SAP	Statistical Analysis Plan
SHR	Sub-distribution Hazard Ratio
SOP	Standard Operating Procedure
SOFA	Sequential Organ Failure Assessment
TMG	Trial Management Group
TSC	Trial Steering Committee
VAP	Ventilator-Associated Pneumonia
WCTU	Warwick Clinical Trials Unit

1. BACKGROUND

1.1 Epidemiology and burden of the condition

Care of the critically ill typically occurs in the intensive care unit (ICU), although it may commence elsewhere, such as the operating theatre or emergency department. If a patient cannot breathe adequately, they may be assisted by mechanical ventilation. This involves placing a tube into the trachea (endotracheal tube (ETT)), which connects to a ventilator. This system ‘takes over’ breathing for the patient. In the UK, over 60,000 adults receive invasive ventilation each year[1], with most of these surviving to leave hospital (66%)[2]. Mechanical ventilation is known to be associated with some clinically important unwanted effects; one is Ventilator-Associated Pneumonia (VAP). Patients who develop VAP have a protracted ICU stay and worse outcome. In addition to the personal cost and risk for each patient, there are significant healthcare costs associated with a protracted stay on ICU, with each day of care costing around £1500. [3, 4].

VAP is the most common Hospital Acquired Infection (HAI) in ICUs occurring in ~30% of mechanically ventilated patients [5-8]. This increased to 45% during the COVID-19 pandemic.[9] A new class of endotracheal tube aimed at providing advanced airway protection may significantly reduce the incidence of VAP (pneumonia occurring >48 hours after intubation)[10] and in turn the length of mechanical ventilation and stay on ICU. Consequently, reducing VAP incidence is important to patients, clinicians, and policy makers.

The National Institute for Health and Care Excellence (NICE) produced medical technologies guidance 48, (April 2020) [11], highlighting the potential for a new ETT, an advanced airway protection device, to prevent Ventilator Associated Pneumonia[11]. However, the current evidence base is not strong enough for formal NICE approval. Therefore, NICE have recommended definitive research to assess the clinical and cost effectiveness of such advanced airway devices in NHS critical care. NICE have identified the PneuX system as the only current example of an advanced airways protection system, that has the best current evidence for the potential to reduce ventilator associated pneumonia and in turn reduce length of time on a ventilator.

1.2 Research Question

In critically ill adults who require invasive mechanical ventilation (population), does the use of an advanced airways protection device (intervention) compared with the conventional endotracheal tubes (comparator) reduce the duration of mechanical ventilation (primary outcome)?

1.3 Need for a trial

The James Lind Priority Setting Partnership for intensive care identified “what is the best way to prevent, diagnose and treat hospital acquired infections” as a top-ten research priority. Infections in the critically ill can significantly impact outcomes. ICU is an expensive and scarce resource such that any reduction in stay could save money and ensure bed capacity for other patients.

Various ETT devices have been tested to reduce the possibility of secretion aspiration from the upper airway, with the hypothesis that this will reduce VAP. These include the importance of maintaining cuff pressure [1, 2], the active removal of secretions above the endotracheal tube cuff and below the vocal cords (sub-glottic suction) [3] and a cuff design that reduces microchannels formation, down which infectious material can pass into the lungs leading to pneumonia[4].

These approaches have been consolidated within new advanced airways protection device(s) as recently as April 2020 identified and reviewed by NICE[5].

In this NICE review, the clinical safety and efficacy was identified from three prospective studies[6-9] that included 341 adult ICU patients. It also highlighted a potential average saving of £738 per patient [10]. The resulting NICE Medical Technologies Guidance (MTG48) recommends a definitive clinical and cost effectiveness randomised controlled trial be performed in NHS care, and there are currently no such studies registered or planned (UK or internationally).

We conducted a new (October - November 2022) national survey of critical care clinicians (n=144) which reported that 35% of respondents intubate critically unwell patients with a standard ETT, and 65% intubate patients with a basic ETT with subglottic suction. Only 20% of respondents measure continuous cuff pressure. Venner (manufacturers of NICE recommended airways system) have confirmed this advanced airways protection device is only used in two UK hospitals. At present, no other comparable ETTs are available on the UK market at present for use in the NHS.

1.4 Ethical considerations

We will conduct the trial in accordance with the ethical principles of the Declaration of Helsinki and Good Clinical Practice. The trial and supporting documents will be submitted to the Sponsor, Research Ethics Committee and Health Research Authority for approval prior to commencing any trial activities.

In collaboration with patient and public colleagues, we will develop participant information that is succinct, relevant and user-friendly in line with Health Research Authority guidance on proportionate consent [11]. We have developed procedures in line with the Mental Capacity Act 2005 (and equivalent Scottish legislation, where possible) to enable all patients requiring tracheal intubation to participate in the study, ranging from patients undergoing elective tracheal intubation (e.g. patients undergoing surgery) where we will seek prior informed consent to those patients requiring emergency tracheal intubation where we will enrol patients initially under a deferred consent model.

Where the patient's consent was not sought prior to enrolment, we will seek this at the earliest reasonable and practical opportunity once the patient has regained capacity. Warwick Clinical Trials Unit is extremely experienced in delivering trials in unscheduled care with these consent models.

1.5 CONSORT

The trial will be reported in line with the CONSORT (*Consolidated Standards of Reporting Trials*) statement (*BMJ* 2010;340:c869).

[figure not shown]
1.6 Confederation of Respiratory Critical Care Trials

PROTECT Airways sits as one of four trial domains within the Confederation of Respiratory Critical Care Trials (CoReCCT). The confederation was established as a novel concept to group a range of respiratory critical care trials with an overarching aim to streamline trial delivery across areas such as governance, contracting, and data collection. The overriding objective is to improve deliverability by minimising burden on participating sites and participants.

2. TRIAL DESIGN

2.1 Trial summary and flow diagram

Figure 1 Trial flow diagram

^a in Scotland referred to as welfare guardian/nearest relative

^b not in Scotland

^c within 30 days of randomisation

2.2 Internal pilot

The main trial will be preceded by an internal pilot study of 9 months duration. This will follow the same processes as the main trial. All patients recruited in the pilot study will be included in the final analysis and this will run seamlessly into the main trial. The pilot study will aim to take place in 32 representative sites. We aim to recruit 220 patients, representing 10% of the total study sample. The aim of the pilot study will be to audit: (a) screening data and assess reasons for exclusion of patients; (b) site and patient recruitment; (c) treatment delivery and fidelity; (d) protocol adherence; (e) unplanned cross-overs; (f) implementation of the training; (g) protocol implementation, using screening logs and case report forms (CRFs); (h) data completeness.

Table 1: Criteria for progression from pilot study to main trial

	Red	Amber	Green
RECRUITMENT			
% Threshold	<50%	50-99%	100%
Sites recruited	<16	16-31	32
Total number of patients recruited	<110	110-219	220
COMPLIANCE/ADHERENCE (of those recruited)			
% Threshold	<50%	50-79%	80-100%

Success criteria for recruitment will be (a) 100% recruitment: progress to main trial; (b) 50-99% recruitment: progress to main trial with review of screening log and protocol and explore the possibility of additional sites; (c) less than 50% recruitment: progression to main trial not anticipated.

Success criteria for protocol adherence and fidelity to the intervention: (a) 80-100% adherence: progress to main trial; (b) 50-79% adherence: progress to main trial with intensive efforts to improve adherence; (c) < 50% adherence: progression not anticipated.

These criteria will be reviewed by the Data Monitoring Committee (DMC) and the Trial Steering Committee (TSC) in association with the health technology assessment (HTA) secretariat.

2.3 Aims and objectives

Objectives:

- (1) Conduct an internal pilot study to confirm the feasibility of a large-scale multicentre trial.
- (2) To conduct a UK-wide multi-centre, open-label, pragmatic, individually randomised, parallel group trial and economic evaluation to determine the clinical and cost effectiveness of an advanced airways protection device versus conventional endotracheal tubes (with and without basic subglottic manual suction and standard cuff) in patients with respiratory failure requiring mechanical ventilation. The outcomes are duration of mechanical ventilation, survival, ICU, and hospital stay outcomes and health-related quality of life.
- (3) Estimate, in an integrated economic evaluation, the cost-effectiveness of an advanced airways protection device versus the conventional endotracheal tubes.

Justification of outcomes

We have worked with patients, the public, researchers and clinicians to determine both our primary and secondary outcomes. This clinical effectiveness trial comprises key core outcomes from the Core Outcomes in Ventilation Trials (COVent) core outcome set and NICE guidelines for ventilation trials and NICE guidelines [5, 12, 13].

Primary effectiveness outcome

The primary variable (outcome) of interest is the duration of mechanical ventilation as measured from time from randomisation to first successful unassisted breathing, measured in days. This outcome is one of the 'COVenT' core outcomes for trials of interventions intended to modify the duration of mechanical ventilation[14]. To clarify:

- Unassisted breathing is defined as no inspiratory support or extracorporeal lung support
- Success is defined as maintaining unassisted breathing at 48 hours.
- Duration includes time receiving extracorporeal lung support, invasive mechanical ventilation and non-invasive ventilation delivering volume or pressure support ventilation.
- Duration excludes time receiving high-flow oxygen therapy and continuous positive airway pressure.
- Patients with a tracheostomy in situ may still achieve successful unassisted breathing.

Secondary outcomes - refer to CoReCCT master protocol for core clinical outcome set.

Effectiveness

- *Duration of endotracheal intubation*: time from randomisation to endotracheal extubation (in hours).
- Ventilator Associated Pneumonia (VAP): Diagnosed by treating clinician with commencement of antibiotics [16] from randomisation up to ICU discharge.
- Hospital Acquired pneumonia (HAP) following extubation- clinician diagnosis and commencement of antibiotics from randomisation up to ICU discharge.

Safety Outcome Measures

Reportable safety events are described in section 7 of the CoReCCT Master Protocol.

Adverse event rates, including device-related

Adverse event rates related to endotracheal tube intubation within 1 hour of intubation, or tube change if allocated to intervention arm:

- *Traumatic insertion, bleeding*
- *Injury to the throat or trachea*
- *Dental damage*
- *Failed intubation*
- *Aspiration during intubation*
- *Pneumothorax*
- *Obstruction or kinking of the endotracheal tube*
- *Cuff leak*
- *Unintentional extubation*

Adverse event rates related to endotracheal tube intubation after one hour of intubation, or tube change if allocated to intervention arm, up to ICU discharge:

- *Tracheal stenosis*
- *Vocal cord injury / paralysis / Arytenoid dislocation*
- *Hoarse voice / voice changes*
- *Sinusitis*
- *Laryngo-tracheal stenosis*
- *Tracheomalacia*
- *Obstructive fibrinous tracheal pseudo membrane*
- *Pressure injuries related to tube securing or pressure from tracheal tube*

- *Tracheo-oesophageal fistula*
- *C-spine and spinal cord injuries due to intubation*

Patient reported and health-economics outcomes:

- Costs associated with use of NHS & personal social services (PSS) resources arising during hospital stay and after hospital discharge; personal expenditures (out-of-pocket costs) incurred by patients after hospital discharge. (also see section Health Economic Evaluation).
- Health-related quality of life using a widely used and recommended preference-based quality of life instrument (EQ-5D-5L) collected at 2 and 6 months.

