2.4.2 Exclusion criteria

1. Intubated for more than 24 hours prior to randomisation
2. Treatment withdrawal anticipated within next 24 hours post randomisation
3. Presence of tracheostomy at screening

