2.9 Trial treatments / intervention

- Intervention: A CE-marked advanced airways protection device (Venner PneuX™)
- Comparator: standard of care, conventional endotracheal tube (with or without basic subglottic suction and standard cuff).

Both the intervention and comparator group will receive standard care for mechanically ventilated patients, as directed by the clinical team. In line with the pragmatic nature of the trial, any escalation or de-escalation of standard treatment will be at the discretion of the clinical team, including oxygen therapy titration and use of non-invasive respiratory strategies. The treatment (comparator or intervention) will continue until:

- Successful unassisted breathing (no further requirement for mechanical ventilation)
- Trial intervention-related serious adverse event
- Death or discontinuation of active treatment

If the participant is extubated and then subsequently requires re-intubating:

1. If less than 48 hours from randomisation should be done using the intervention tube if allocated to the intervention arm.
2. If greater than 48 hours from randomisation should be done according to clinicians discretion.

Intervention

An advanced airways protection device consists of a flexible ETT with ports for subglottic suction/irrigation as well as a port to attach to an electronic system to maintain cuff pressure. The Venner PneuX™ device was recommended for testing in a large scale clinical trial by NICE in MTG48[5]. It is the only advanced airway system currently available in the NHS. Venner PneuX™ device is available in various sizes. We will test this system and the findings will be generalisable to future devices with similar design features and capabilities.

The Venner PneuX™ device is a flexible armoured ETT. It has a low-volume, low pressure cuff, that inflates uniformly without folds or creases. The key innovative design is the cuff which does not form microchannels and this prevents micro-aspiration during long term ventilation [18]. The endotracheal cuff and pilot balloon is connected to an electronic system that continuously maintains, monitors, and regulates the pre-set cuff pressure. It has three sub-glottic suction ports around the circumference to ensure that at least one port is patent for suctioning. Sub-glottic suction ports can facilitate irrigation and aspiration of secretions from the subglottic space.

Figure 2 Venner PneuX™ device - an advanced airways protection system

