6.2.2 Statistical analysis plan

Primary outcome analyses

The outcome summaries and analyses will adopt the Estimand framework (as cited by the ICH E9 (R1) addendum on Estimand and sensitivity analyses in clinical trials) [33].

Summary measure and the primary Estimand: The duration of mechanical ventilation (in days) will be summarised using median, interquartile range, mean and standard deviation. The statistical analysis for this outcome will be done using the treatment policy strategy (i.e. intention to treat). Time-to event (survival models) analysis will be used to estimate the treatment effect by summarising hazards odds ratios (and 95% confidence intervals), using both unadjusted and adjusted (for site and adjusting for e.g. age and illness severity (APACHE II)) estimates. Kaplan-Meier plots will be used to display the duration of ventilation accommodating for the censored values. Intercurrent events (ICEs) and strategies for handling ICEs: post-randomisation events that may affect the interpretation of the primary outcome will include: (a) death (ICE 1); (b) cross-over (ICE 2); (b) non-compliance (including discontinuation of treatment) (ICE 3). The ICE 1 will be analysed using a composite strategy and applying competing risk models. Fine and Gray competing risk regression will be used to assess duration of ventilation, in the presence of death[34]. Competing risk regression models address the situation when more than one mutually exclusive endpoint is possible: in this case, successful extubation or death. This analysis provides a sub-distribution hazard ratio (SHR), the magnitude of which is affected by both the time to coming off the ventilator and the probability of death. SHR assesses the association between an intervention and extubation, accounting for the existence of the alternative outcome of death. The ICE 2 and ICE 3 will be analysed using the principal stratum strategy. For the ICE 2, we will

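### The primary outcome ignores why support stopped, so extubation on withdrawal of active treatment counts as liberation if the patient lives 48 hours

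*Protocol*

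**What the plan says.** The primary outcome in section 2.3 is "duration of mechanical ventilation as measured from time from randomisation to first successful unassisted breathing, measured in days". Two statements then fix the event. The first is "Unassisted breathing is defined as no inspiratory support or extracorporeal lung support". The second is "Success is defined as maintaining unassisted breathing at 48 hours". The trial summary table points to this place as the "full definition in section 2.3", so nothing fuller is to be expected elsewhere in this protocol.

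Section 2.9 lists the points at which trial treatment ends. One is "Successful unassisted breathing (no further requirement for mechanical ventilation)". A separate entry is "Death or discontinuation of active treatment". The protocol therefore foresees that active treatment may be stopped after randomisation, and in that list it keeps this apart from success.

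Section 6.2.2 says of death: "The ICE 1 will be analysed using a composite strategy and applying competing risk models". The model is Fine and Gray, with successful extubation and death as the two mutually exclusive endpoints. Discontinuation of treatment appears there only as a form of non-compliance (ICE 3), to be handled by a complier average causal effect analysis.

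**The concern.** Neither statement in section 2.3 depends on the reason for ending support. A patient extubated when active treatment is withdrawn, who is still breathing without support 48 hours later, meets both. The event is timed at the withdrawal. Because the model follows each patient to the first event, a death on day 3 or day 5 after extubation no longer enters as the competing event. Some patients who die are then counted as liberated, possibly early.

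Two things are at stake. First, these events carry no information about whether the device shortens the need for ventilation, so they dilute the estimated effect. Second, whether and when to withdraw treatment is decided by clinicians who know the allocation. If that practice differed by arm, the primary estimate would be biased. Section 2.10 relies on an objective primary outcome as a protection against the lack of blinding, and this is a point where the outcome depends on a clinical decision.

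**Working it through.** **Step 1. Does any other rule catch the case?**

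- Exclusion criterion 2 reads "Treatment withdrawal anticipated within next 24 hours post randomisation". It covers only what is foreseen for the first day.
- The wording in brackets in section 2.9, on ventilation being no longer required, would exclude these patients if it applied to the outcome. It governs when trial treatment ends.
- ICE 3 concerns compliance with the allocated device. It does not change who counts as a success.
- Death as the competing event catches patients who die before the 48-hour condition is met. It does not catch those who die afterwards.

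No rule in the protocol removes the case.

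**Step 2. The planned sample size.** Inputs from section 6.1: hazard ratio 1.2, Weibull shape 0.901, power 90%, alpha 5% (taken as two-sided), mortality 25.6%, withdrawal from the trial 3%.

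- Adjusted hazard ratio: 1.2^0.901 = 1.1785.
- Freedman: events = (1.960 + 1.282)² × [(1.1785 + 1)/(1.1785 − 1)]² = 1565.
- Total: 1565/(1 − 0.256 − 0.03) = 1565/0.714 = 2192, against 2194 stated. The Schoenfeld formula gives 1558 events and 2182 patients.

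The stated figure is reproduced. All 25.6% of deaths are removed as non-events, so the calculation assumes that no patient who dies contributes a liberation. Expected events are 2194 × 0.714 = 1566.

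**Step 3. How many patients?** The documents give no rate of extubation on withdrawal, and none of survival to 48 hours after it. Assumed ranges: 50-80% of deaths follow extubation on withdrawal, and 5-10% of those patients live at least 48 hours.

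- Low: 2194 × 0.256 × 0.50 × 0.05 = 14, and 14/1566 = 0.9%.
- High: 2194 × 0.256 × 0.80 × 0.10 = 45, and 45/1566 = 2.9%.

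**Step 4. Effect on power if unrelated to arm.** Here the two losses are multiplied: true events D = 2194 × 0.97 × 0.744 = 1583. With F added events that carry no treatment effect, ln HR becomes ln(1.1785) × D/(D + F). Schoenfeld power is Φ(½ × √(D + F) × ln HR − 1.96).

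| Share of deaths misclassified | F | Share of all events | Diluted HR | Power |
|---|---|---|---|---|
| 0% | 0 | 0% | 1.1785 | 90.5% |
| 5% | 27 | 1.7% | 1.175 | 90.0% |
| 10% | 54 | 3.3% | 1.172 | 89.5% |
| 20% | 109 | 6.4% | 1.166 | 88.5% |
| 30% | 163 | 9.4% | 1.161 | 87.5% |

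The assumed ranges in step 3 correspond to 2.5% (0.50 × 0.05) to 8% (0.80 × 0.10) of deaths. That lies above the 10% row, so the loss is under about 1 point.

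**Step 5. If related to arm.** The error is then bias. Neither its size nor its direction can be derived from the documents.

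**The case against.** The strongest reply is that this is a small matter of wording. The rates are assumed, the power loss is under about 1 point within the assumed range, and no stated figure changes. Event coding is often left to the statistical analysis plan, and that plan or the master protocol may contain a rule. This stands as to size. It does not remove the point, because the protocol names section 2.3 as the full definition and the rule there classes these patients as successes.

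A second reply is that excluding them makes success depend on a reason recorded by unblinded staff. That is fair, and it is why the fix includes a sensitivity analysis under the current definition.

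A reader might also infer more than the documents support:

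- That the arms are shown to be misclassified differently. No mechanism or figure supports this. Section 2.10 plans data on readiness to extubate and on why extubation did not go as planned, with checks against hourly charts. These bear on performance bias, although the section does not mention recording why support was ended.
- That the definition runs against the stated aim of the composite strategy. Section 6.2.2 names the strategy but states no such aim.
- That later deaths are lost to the trial. All-cause mortality is recorded at ICU discharge, hospital discharge, 2 months and 6 months (section 4.1). Only the primary time-to-event analysis is affected. In that analysis any death after liberation is passed over, since the outcome is time to first success.
- That success is a single check at 48 hours. The word used is maintaining, so a patient who returns to support or dies before then does not qualify.

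**Conclusion.** The point holds as a flaw in the outcome definition. Section 2.3 scores extubation on withdrawal of active treatment followed by 48-hour survival as liberation, while section 2.9 treats discontinuation of active treatment as something different from success. The likely extent is 14-45 of 2194 patients, or 0.9-2.9% of about 1566 events. This rests on the protocol's 25.6% mortality and on two assumed ranges (50-80% and 5-10%) that the documents do not give. If unrelated to arm, it costs under about 1 point of power. Bias between arms is possible because the trial is open-label, but it is not shown and its direction is unknown. The change is worth making because every error runs from not liberated to liberated and the correction is cheap. It does not threaten the trial.

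**What to change.** Reconcile sections 2.3, 2.9 and 6.2.2 for outcome classification only. No clinical rule needs to change.

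1. In section 2.3, state that unassisted breathing which begins with documented discontinuation of active treatment is not success.
2. In section 6.2.2, state one rule: such patients have the competing event and are counted as not liberated. A rule that depended on death in hospital would class differently those who survive to discharge, so the two should not be offered as alternatives.
3. Record the reason for ending ventilation on the CRF. The protocol mentions no such field, so it should be treated as a new item unless the CRF already has it.
4. Report a sensitivity analysis under the current definition, which ignores the reason, because unblinded staff record it.

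The cost is a short addition to each of the two sections, one CRF item, some reliance on an unblinded reason, and a slightly lower success count. The sample size stays at 2194, since the calculation already treats all deaths as non-events. The change should be made before unblinded outcome data are reviewed.
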